Our primary outcome measure is self-management ability as measured by the (PAM) [17,18]. In a study by Turner et al., it was reported that patients with chronic diseases who completed a 7-week self-management program would have their mean PAM score improve from

52.2 to 60.2 at 6 months (standardized effect size = 0.65) [34]. Based on a difference of 8 points, an estimated SD of 12.4, and a 2-tailed analysis of covariance (ANOVA), a total of 102 participants (51 per group) would be needed (90% power; α -level 0.05). We plan to recruit a total sample size of 134, with 67 participants in each group, to allow for a ~24% attrition rate.

For the implementation assessment, we will conduct qualitative interviews with 7-10 participants in each of the 4 purposive sampling strata, including gender (2) and experience in using health-related apps (2). Hence, 28 – 40 people will be interviewed.

Data Analysis

The data collected will be de-identified and password protected. All research personnel involved with data analysis will have access to the data files. The study coordinator will oversee the data sharing process.

Efficacy Analyses

The intervention efficacy will follow an intention-to-treat approach. We will analyze the outcomes measured at weeks 26 and 52 in the II and DI groups. We will employ Generalized Linear Mixed-effect Models (GLMM), adjusting for baseline value on the outcome variable and sex as covariates. These models are the most efficient and recommended statistical methods for analyzing longitudinal clinical trial data with missing data [35, 36] and can account for data missing at random without the need to perform explicit imputations of the missing values [37]. Binary indicators of group and months since baseline, will allow us to test their interaction ($p < 0.05$ for 2-tailed Wald test), which addresses if the outcome post-intervention is significantly better in the II than DI group. Data transformation, if needed, will be applied to continuous

outcomes to satisfy the assumption of normality. The sandwich estimators for GLMMs [38] will be used to compute empirical standard errors that are robust to model specifications and distributional assumptions. An unstructured variance–covariance matrix will be used to model the within-subject error variance-covariance for continuous outcomes. The quality of statistical inferences will be substantiated through rigorous model checking and validation techniques.

Implementation Analysis

For the qualitative interviews, we will conduct an iterative content analysis, whereby codes will be identified and revised as interviews are analyzed. Initial open coding will be followed by clustering the labels into thematic categories [39]. Quotes representative of the thematic categories will be identified to illustrate experiences of participants with the intervention, as well as barriers and facilitators in meeting their physical activity goals. If distinct themes based on gender or age are apparent, data will be reanalyzed within subgroups. Descriptive analysis will be conducted for all participants' usage data from the OPERAS app.

An iterative content analysis will be used to identify and revise codes in the qualitative interviews. We will start with an initial open coding and then cluster the labels into thematic categories [40]. Quotes representative of the thematic categories will be identified to illustrate experiences of participants in using OPERAS, as well as barriers and facilitators in using the program. We will reanalyze the data within subgroups if there are distinct themes based on gender or age. We will also conduct a descriptive analysis for all participants' usage data.

Reference List

1. Wagner EH. Managed care and chronic illness: health services research needs. *Health Serv Res.* 1997;32(5):702-14.
3. van den Bart BJ, Zwikker HE, Van den Ende CH. Medication adherence in patients with rheumatoid arthritis: a critical appraisal of the existing literature. *Expert Rev Clin Immunol* 2012;8:337-51.

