participants to stop their medical treatments and non-pharmacological care during their participation in the study.

Measurements

All participants will be assessed 3 times throughout the study: at baseline (T0), week 27 (T1), and week 53 (T2). Baseline measurements will be completed before randomization. Research personnel performing data analysis will be blinded to the group assignment. We will not be blinding the group assignment to the study coordinator, who will be facilitating delivery of the intervention, nor the participants who will be receiving it.

Outcomes

Primary Outcome

Self-management ability will be assessed through the Patient Activation Measure (PAM), a 13-item self-reported measure of individual's confidence in managing chronic diseases [17,18]. Each item has a 4-point response, with 1 being strongly disagree and 4 being strongly agree, and the aggregate raw score is converted to 0-100 [15]. Hibbard et al [17] described a 4-stage activation model based on the standardized scores of PAM: 1) believing an active role is important (PAM score <47); 2) having confidence and knowledge to take action (47.1 - 55.1); 3) taking action (55.2 - 67); and 4) maintaining healthy behaviors despite setbacks (> 67.1). PAM has demonstrated internal consistency (Chronbach's $\alpha > 0.85$) [17], and construct validity with health status measures (e.g., SF-36 [24]) and healthy behaviours such as exercise, healthy eating and medication adherence [19].

Secondary Outcomes

We will assess disease status through the RADAI which categorizes disease activity into remission, low, moderate, and high states [20]. RADAI has 5 components, including 1) global disease activity; 2) joint tenderness/swelling; 3) pain; 4) morning stiffness; and 5) number/severity of painful joints. Its validity was supported by moderate correlations with physicians' assessment of disease activity ($r = 0.54$), swollen joint count ($r = 0.54$), and C-reactive protein value ($r = 0.43$) [18].

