Pain will be measured with the McGill Pain Questionnaire (MPQ-SF), which consists of 15-pain related words that can be rated from 0 to 3, with the higher number being more severe [21]. We will measure fatigue using the Fatigue Severity Scale (FSS), a 9-item questionnaire that has demonstrated internal consistency (Cronbach's $\alpha=0.89$) [22]. The FSS is also moderately correlated with pain ($r=0.68$) and depression ($r=0.46$) [23]. We will also assess participants' mood using the Patient Health Questionnaire-9 (PHQ-9) [24] which consists of 9 questions that correspond to the diagnostic criteria for major depressive disorder. A total score of greater than 11 indicates the presence of major depressive disorder [25].

The Self-Reported Habit Index (SRHI) will be used to measure characteristics of habitual behavior. It is a 12-item scale, rated on a 7-point Likert scale, with higher scores indicating a stronger habit or behavior that is done frequently, automatically, and done without thinking about it [26, 27]. Participants will rate their strength of habit for 3 specific behaviors, including sitting during leisure time at home, sitting during usual occupational activities, and walking outside for 10 minutes or more.

We will measure participants' time spent in physical activity and sedentary activity with SenseWear Mini. It integrates tri-axial accelerometer data, physiological sensor data and

personal demographic information to estimate steps, energy expenditure and Metabolic Equivalent of Tasks (METs). Tierney et al. [28] has showed that the SenseWear is an appropriate tool in estimating energy expenditure during activities of daily living in people with arthritis (intraclass correlation coefficient (ICC) = 0.72). Participants will wear the SenseWear monitor over their triceps on the non-dominant arm for 7 days. Almeida et al [29] recommended that a minimum of 4 days is required to reliably assess energy expenditure from different levels of physical activity in people with RA (ICC > 0.80).

We will calculate: 1) the mean time spent in bouts MVPA per day. A bout is defined as ≥ 10 consecutive minutes at the level of ≥ 3 METs (i.e., the lower bound of MVPA), with allowance for interruption of up to one minute below the threshold [30]. 2) Mean daily time spent in sedentary behaviours, with an energy expenditure of ≤ 1.5 METs, occurring in bouts of > 20 minutes during waking hours [31, 32].

Implementation Assessment

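### The missing-data assurance covers follow-up values only: with baseline as a covariate, a participant without a usable SenseWear baseline adds nothing to the activity analyses

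*Combined protocol and SAP*

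**What the plan says.** Four statements under Data Analysis, Efficacy Analyses, work together.

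- Principle: "The intervention efficacy will follow an intention-to-treat approach".
- Response: "We will analyze the outcomes measured at weeks 26 and 52 in the II and DI groups". These are the T1 and T2 visits, which Fig 1 and Measurements place at weeks 27 and 53.
- Adjustment: the model is fitted "adjusting for baseline value on the outcome variable and sex as covariates".
- Missing data: the chosen models "can account for data missing at random without the need to perform explicit imputations of the missing values".

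Three statements elsewhere bear on how often a baseline could be missing.

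- Measurements: "Baseline measurements will be completed before randomization". Fig 1 lists SenseWear at T0, T1 and T2.
- Secondary Outcomes: "Participants will wear the SenseWear monitor over their triceps on the non-dominant arm for 7 days".
- The same section reports that a published study "recommended that a minimum of 4 days is required to reliably assess energy expenditure from different levels of physical activity". It does not adopt this as the trial's own validity rule.

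The eligibility criteria under Participants do not mention a usable recording. No section says what happens when a baseline value is missing.

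**The concern.** A likelihood-based mixed model uses whatever responses a person has, so a missed T1 or T2 visit needs no imputation if the data are missing at random. It does nothing for a missing regressor. Here baseline is a regressor and not part of the response, so a person without it has no usable row at either follow-up visit unless some further step is taken. The plan names no such step and says that none is needed.

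The SenseWear outcomes are the ones most exposed. A questionnaire is normally either filled in or not, whereas a week of monitor wear can be attempted and still yield too little to use. Bouted activity and sedentary time are also the trial's only device-measured outcomes. If some baselines prove unusable, randomized people with valid follow-up recordings would leave those two analyses, although the plan describes its efficacy analysis as intention-to-treat without qualification.

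**Working it through.** **The plan's own figures.** The plan gives no figure for missing baselines. Its sample size, which sets the counts below, reproduces. With a difference of 8, SD 12.4, two-sided 5% alpha and 90% power, n per arm = 2 × (1.960 + 1.282)² × 12.4² / 8² = 50.5, rounded up to 51, or 102 in total. Recruiting 134 allows for 1 − 102/134 = 23.9% attrition, as stated.

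**Mechanism.** One simulated data set of 134 people had 10 without a baseline and 128 with at least one follow-up value. With baseline as a covariate, 118 people entered the model. The missing 128 − 118 = 10 were exactly those without a baseline, and all had follow-up data. With baseline moved into the response, all 134 contributed.

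**Head count under an assumed share m of unusable baselines.** 134 × m gives 0 people at 0%, 7 at 5%, 13 at 10% and 27 at 20%. If attrition acts independently, 102 × (1 − m) leaves about 102, 97, 92 and 82 people for the SenseWear outcomes.

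**Precision.** Let r be the correlation between baseline and follow-up, and set the outcome variance to 1. A person with a baseline has residual variance 1 − r²; a person without one has variance 1. In units of one fully observed person:

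- information after dropping = 1 − m
- information under a joint model = (1 − m) + m(1 − r²)
- SE ratio, dropping to joint = √{[(1 − m) + m(1 − r²)] / (1 − m)}

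| m (assumed) | r (assumed) | Dropping | Joint | Information ratio | SE ratio |
|---|---|---|---|---|---|
| 0% | any | 1.000 | 1.000 | 1.000 | 1.000 |
| 10% | 0.5 | 0.900 | 0.975 | 1.083 | 1.041 |
| 10% | 0.7 | 0.900 | 0.951 | 1.057 | 1.028 |
| 20% | 0.5 | 0.800 | 0.950 | 1.188 | 1.090 |
| 20% | 0.7 | 0.800 | 0.902 | 1.128 | 1.062 |

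These ratios are for the arm difference at one follow-up visit. They do not size the loss for the group-by-time interaction test.

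**Bias.** In simulations of 102 people with baseline missing at random (20,000 runs per setting), dropping moved the arm contrast by no more than 0.002 SD.

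**Filling with the pooled baseline mean.** With no missing-value indicator, the variance of the contrast is proportional to (1 − m)(1 − r²) + m after filling and to (1 − r²)/(1 − m) after dropping. Filling is the less precise of the two once r exceeds 1/√(2 − m), which is 0.73 at m = 10% and 0.75 at m = 20%. At r = 0.8 and m = 10%, filling gives 0.9 × 0.36 + 0.1 = 0.424 and dropping gives 0.36/0.9 = 0.400.

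**The case against.** The strongest reply is that the problem may never arise. Baseline is to be completed before randomization, SenseWear is scheduled at T0, and no valid-wear rule is adopted, so someone with three days of wear still has a baseline mean and stays in. This stands as a limit on size: the number affected is unknown and zero is admissible. It does not close the gap, because completing a measurement does not guarantee a usable recording, and nothing makes randomization wait for one.

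A reader might infer three stronger things that the documents do not support.

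- *That the plan excludes these people.* It does not say so. The loss follows from the form of the model and from having no rule for this case.
- *That the randomized comparison is biased.* Baseline precedes allocation, so selection on it is unrelated to arm in expectation. This would fail only if usability were judged after allocation by someone who knew the arm.
- *That the avoidable SE loss is 5% at 10% missing and 12% at 20%.* Those figures, 1/√0.9 = 1.05 and 1/√0.8 = 1.12, compare dropping with a complete baseline, which no analysis can restore. The fair comparator is the joint model.

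Two further objections stand in part. Covariate adjustment is an accepted analysis, and the adjustment phrase governs every outcome including PAM, so rewriting it throughout would go further than the problem requires. The activity outcomes are secondary and are not named in the second study objective. Both argue for a narrow change rather than for none.

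**Conclusion.** The concern holds for the two secondary SenseWear outcomes. The missing-data statement is correct for follow-up values and does not extend to a missing baseline covariate. As the model is specified, a randomized participant with follow-up data but no usable baseline is left out. For an assumed 10% or 20% of unusable baselines, the avoidable widening of the standard error is about 3-4% or 6-9% for r between 0.7 and 0.5. At 0% there is none. Both m and r are assumptions, since the documents give neither.

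The consequence is modest: some precision, and an analysed set smaller than the intention-to-treat label implies. The PAM analysis and its sample size are unaffected if the baseline questionnaire is complete.

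**What to change.** Confine the change to bouted activity and sedentary time.

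1. Model T0, T1 and T2 together as responses, with a common T0 mean across arms, sex retained, and the unstructured covariance already planned. Transform skewed activity data as the plan already allows.
2. State that no randomized participant with follow-up data is excluded for lack of a baseline value.
3. Define a usable SenseWear recording, have it judged without knowledge of arm, and report by arm how many participants lack a usable baseline.

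Plain pooled-mean filling should not be the recommended alternative, because it can be less precise than dropping when r exceeds about 0.73-0.75.

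The cost is a few sentences and a few lines of code, with no new data. There is one small downside: the joint model makes a distributional assumption about baseline that covariate adjustment does not need. If every baseline proves usable, the change makes essentially no difference to the arm comparison.

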health on a trial-and-error basis [11]. The current practice relies on patients applying their self-management knowledge and skills in daily life with little feedback on their performance or how their actions affect their health. In light of these findings, we believe that there is a need for a multifaceted approach that provides support in terms of knowledge, skill development and timely advice from health professionals, as well as motivational support for patients to be engaged in their care and to stay physically active.

OPERAS web application

The OPERAS web app was designed to engage patients in monitoring and managing their health. Building from two existing software programs, the Arthritis Health Journal (AHJ) [12] and FitViz [13], OPERAS allows users to track symptoms, self-management goals, medication use, and physical activity. The latter is automatically measured by Fitbit. Using OPERAS, a physiotherapist (PT) will provide remote counselling to guide the user in setting realistic physical activity goals. Based on the users' goals, the PT can adjust parameters of physical activity intensity and duration to provide automated personalized feedback on their goal attainment.

The objectives of this study are to: 1) assess the efficacy of OPERAS at improving self-management ability of people with RA in a 6-month randomized controlled trial (RCT); 2) explore the effect of OPERAS on disease status, pain, fatigue, depressive symptoms, and characteristics of habitual behavior; and 3) assess barriers to implementation and sustainability of OPERAS from the perspectives of participants involved in the study.

Methods/design

Study Design

The *Empowering active self-management of arthritis: Raising the bar with OPERAS (an On-demand Program to Empower Active Self-management)* project will use a mix of quantitative and qualitative research methods. The RCT will employ a delayed control design, whereby participants will be randomly assigned to start the 6-month intervention immediately (Immediate Intervention [II] group) or 6 months later (Delayed Intervention [DI] group) using a 1:1 allocation ratio. Participants will be assessed 3 times throughout the study (Fig. 1.). At the end of the intervention, we will invite a sample of participants to be interviewed regarding their experiences.

Participants

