Fig 1 Standard protocol items: recommendation for interventional trials (SPIRIT) figure

The Intervention

Participants randomized into the II group will receive the 6 month intervention immediately. They will attend a 2-hour in-person session where they will: 1) participate in a group education session from a study PT about self-management and physical activity for people with RA, 2) receive a Fitbit Flex 2 and an orientation to the OPERAS web app, and 3) receive

individual counselling from a PT trained in motivational interviewing [15]. All study PTs will follow the Brief Action Planning approach [16], whereby participants will be guided to set their own physical activity goals, develop an action plan, and identify barriers and solutions.

We will ask participants to wear the Fitbit throughout the intervention period, and use the OPERAS app to record their RA disease activity, symptoms, treatment use, and self-management action plans. If participants experience any discomfort wearing the Fitbit, we will advise them to stop wearing it but continue using the OPERAS web app. Disease activity will be tabulated from participants' self-reported measures, including the Rheumatoid Arthritis Disease Activity Index [RADAI], Visual Analogue Scale [VAS], and the Health Assessment Questionnaire [HAQ]. Participants will record their symptoms twice a week during periods of more active disease (i.e., a disease activity score above 4), and once every 2 weeks during periods of stable disease (i.e. no sudden increases in disease activity score). They will also be asked to log on and review their physical activity goal achievements at least once a week. Participants who have not recorded their disease activity for more than 2 weeks will receive an email reminder from the research team.

II participants will receive a phone call from their PTs at weeks 2, 4, 6, 8, 13 and 26 to review their physical activity goals and accomplishments. PTs will coach participants to modify their goals if they are ready.

The DI group will receive the same intervention in week 27. Participants will receive a monthly newsletter of arthritis news, which are unrelated to disease management prior to the intervention period.

After the six-month intervention period, both II and DI participants can keep the Fitbit and their OPERAS app account, but will not have access to a PT. There is no requirement for

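### The only efficacy test named is a group-by-time interaction over weeks 26 and 52, which does not estimate the 6-month effect because the delayed group is treated before the second visit

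*Combined protocol and SAP*

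**What the plan says.** Objective 1, stated at the end of the OPERAS web application section, is to "assess the efficacy of OPERAS at improving self-management ability of people with RA in a 6-month randomized controlled trial". Under The Intervention, "The DI group will receive the same intervention in week 27". Fig 1 gives DI access to the app and Fitbit from week 27 to week 53. After its own six months, II keeps the app and the Fitbit but no longer has a physiotherapist.

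Under Efficacy Analyses: "We will analyze the outcomes measured at weeks 26 and 52 in the II and DI groups". The mixed model adjusts for the baseline value of the outcome and for sex. The test is then defined: "Binary indicators of group and months since baseline, will allow us to test their interaction", by a two-sided Wald test at 0.05, "which addresses if the outcome post-intervention is significantly better in the II than DI group". No other efficacy test is specified, and no visit is named as primary.

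The Sample Size Calculation assumes a single between-group PAM difference of 8 points with SD 12.4, two-sided alpha 0.05 and 90% power. It arrives at 51 per group (102 in total), raised to 134 for attrition of about 24%.

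**The concern.** Because baseline is a covariate, time has two levels in the model, T1 and T2. The interaction asks whether the II minus DI gap differs between them. At T1 the gap is a randomised comparison of treated with untreated participants. At T2 both groups have had the programme, so the gap reflects how well II has held its gain and how much DI has gained. The interaction combines all three quantities and so does not answer objective 1.

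Two wrong conclusions become possible. A real and lasting 6-month benefit can give a null test, and a significant test can arise with no 6-month benefit. The stated 90% power belongs to a simple two-group difference and does not carry over to this term. With no primary visit named, the choice between T1, T2 and the interaction could also be made after the data are seen.

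**Working it through.** **Inputs.** From the Sample Size Calculation: difference 8, SD 12.4, 51 per group, two-sided alpha 0.05. The correlation ρ between visits is not in the documents. It is assumed equal for all pairs of visits and shown from 0.3 to 0.7.

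**The plan's own figure.** For two means, SE = 12.4 × √(2/51) = 2.456. Then 8/2.456 = 3.258, and 3.258 − 1.960 = 1.298, giving 90.3% power (normal approximation). This reproduces 51 per group. Attrition: 1 − 102/134 = 23.9%, as stated. The sample size therefore fits one group difference at one visit.

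**What the interaction estimates.** Let D1 and D2 be the II minus DI differences at T1 and T2. With T1 as the reference visit, the coefficient is D2 − D1. If II's benefit at T2 is M and DI's gain from treatment is G, then D2 = M − G and the coefficient is M − G − D1. When DI catches up, a benefit at T1 appears as a negative coefficient. Least-squares fits to simulated data (200,000 per arm, baseline as covariate) confirmed this: the group coefficient at T1 stayed at about 8 while the interaction moved between about 0 and −16.

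**Standard errors at 51 per group.**
- Interaction: √(4 × 12.4² × (1 − ρ)/51). At ρ = 0.6 this is √(4 × 153.76 × 0.4/51) = 2.20.
- T1 contrast adjusted for baseline: √(2 × 12.4² × (1 − ρ²)/51). At ρ = 0.6 this is √(2 × 153.76 × 0.64/51) = 1.96.

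**Probability that the interaction test rejects.** Interaction sizes are absolute values.

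| D1 | M (II at T2) | G (DI gain) | D2 | Interaction | ρ = 0.3 | 0.5 | 0.6 | 0.7 |
|---|---|---|---|---|---|---|---|---|
| 8 | 8 | 8 | 0 | 8 | 79% | 90% | 95% | 99% |
| 8 | 4 | 8 | −4 | 12 | 98.5% | >99% | >99% | >99% |
| 8 | 0 | 8 | −8 | 16 | >99% | >99% | >99% | >99% |
| 8 | 8 | 4 | 4 | 4 | 28% | 37% | 45% | 56% |
| 8 | 10 | 6 | 4 | 4 | 28% | 37% | 45% | 56% |
| 8 | 8 | 2 | 6 | 2 | 11% | 13% | 15% | 18% |
| 8 | 8 | 0 | 8 | 0 | 5% | 5% | 5% | 5% |
| 0 | 0 | 4 | −4 | 4 | 28% | 37% | 45% | 56% |

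Example at ρ = 0.6 for an interaction of 4: 4/2.20 = 1.82, and 1.82 − 1.96 = −0.14, giving 45%.

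**The T1 contrast.** In every row with D1 = 8, the baseline-adjusted T1 contrast targets 8. Its power is 93%, 96%, 98% and >99% for ρ = 0.3, 0.5, 0.6 and 0.7, and 90.3% with no credit for baseline. In the last row it rejects 5% of the time, as it should.

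**The case against.** **Another coding.** The phrase about binary indicators could mean dummy variables for each follow-up visit against baseline. The group-by-month-6 term would then be the 6-month effect and the plan's interpretation would be right. But that needs baseline to be a level of time, whereas the section makes it a covariate and analyses only weeks 26 and 52. If this coding was meant, the text still has to be changed.

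**The intended target can be inferred.** Objective 1 speaks of a 6-month trial, and the sample size rests on a PAM change at 6 months. That is fair, but it supports naming T1 as primary. It does not turn the interaction into a T1 contrast.

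**Some scenarios are extreme.** A DI group that gains nothing from the programme that gave II 8 points, or that moves by 4 when II never did, is a boundary case. Drift common to both groups cancels. If DI responds fully and II holds its gain, the interaction does well, and it can have more power than the T1 contrast. This stands: the loss of power is not uniform. The defect lies in what is estimated. Partial response in DI is plausible, though, and there power is 28% to 56%.

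**The 98% for the T1 contrast flatters the fix.** It assumes a correlation of 0.6 and that 12.4 is the unadjusted SD, which the plan does not say. About 90% is the cautious figure, and it equals the power planned.

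**Secondary outcomes.** Objective 2 is exploratory, so using the T1 contrast there is a matter of consistency more than necessity.

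**Conclusion.** The concern holds, and this must be fixed before analysis. As written, the only specified test measures the change in the II minus DI gap after DI has been treated, not the 6-month effect. Its size equals the 6-month effect only in special cases, such as a zero gap at T2, and then with the sign reversed. Across the scenarios with a true 8-point T1 effect, the interaction runs from 0 to 16 points and its power from 5% to above 99%. These power figures rest on SD 12.4, 51 per group and an assumed correlation of 0.3 to 0.7. The mismatch between the test and the objective follows from the wording and the design alone and needs none of these assumptions.

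**What to change.** In Efficacy Analyses, state the primary estimand as the II minus DI adjusted mean difference in PAM at T1. Test it as the group contrast at T1 from the model already planned: baseline, sex, group, time, group-by-time, unstructured covariance. Use the same T1 contrast for the secondary outcomes. Keep the T2 difference and the interaction as secondary, described as maintenance in II and uptake in DI, and do not read either as efficacy.

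In the same edit, reconcile weeks 26 and 52 in the analysis section with weeks 27 and 53 under Measurements. Because Fig 1 places T1 and the DI education session in the same week, state that T1 is measured before DI starts.

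The cost is one paragraph of text, written before the data are analysed. The model, the data collected and the sample size (102 evaluable, 134 recruited) stay as they are. The only loss is that T2 becomes secondary.
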